12.7.4. Reporting Procedures for Unanticipated Problems, Adverse Events, and Adverse Device Effects

Principal investigators should notify and local IRB, in an expedited manner, of those events related to study participation that are unforeseen and indicate that participants or others are at increased risk of harm.

Researchers should submit reports of the following problems:

Any AE/ADE or UP (regardless of whether the event is serious or non-serious, on-site or off-site) that occurs any time during or after the research study, which in the opinion of the principal investigator is:

Unexpected (An event is “unexpected” when its specificity and severity are not accurately reflected in the protocol-related documents, such as the IRB-approved research protocol, any applicable investigator brochure, and the current IRB-approved informed consent document and other relevant sources of information, such as product labeling and package inserts.)

AND

Related to the research procedures (An event is “related to the research procedures” if in the opinion of the principal investigator, the event was more likely than not to be caused by the research procedures.)

AND

Suggests that the research places subjects or others at a greater risk of harm (including physical, psychological, economic, or social harm) than was previously known or recognized.

Additionally, all adverse events/adverse device effects shall be documented by the PI team, assessed, and shared with. All Serious Adverse Events will be forwarded to **Merck Worldwide Product Safety**.

What Event is Reported	By Whom is Event Reported	To Whom is Event Reported	When is Event Reported
-------------------------------	----------------------------------	----------------------------------	-------------------------------

Fatal unexpected, suspected serious adverse event (SAE/ADE – death that is unexpected and poss/prob/def related to the research)	Investigator	Local IRB	Within 24 hours of initial receipt of information
Life-threatening unexpected, suspected serious adverse reactions (SAE/ADE- life-threatening, unexpected, poss/prob/def related to the research)	Investigator	Local IRB	
Non-fatal, non-life-threatening unexpected, suspected serious adverse reactions (SAE/ADE – unexpected, poss/prob/def related, non-life-threatening hospitalization, prolonged hospitalization, disability/incapacity/birth defects, important medical event)	Investigator	Local IRB	Within 3 calendar days of initial receipt of information
Unanticipated Problem that is not an SAE (AE/ADE or non-AE, unexpected, poss/prob/def related and suggests greater risk of harm) e.g. Development of moderate hypersomnia that resolve after discontinuing drug. This AE/ADE although not-serious, is not listed as an expected event in the consent. Thus it is an AE that is unexpected, possibly related (resolved after coming off drug), and places subject(s) at greater risk of harm than previously known	Investigator	Local IRB	Within 10 calendar days of initial receipt of information

12.7.4.1. Reporting Process

UPs posing risks to subjects or others as noted above will be reported to local IRB using a Medwatch or CIOMS report of the event (including a description of the event with information regarding its fulfillment of the above criteria, follow-up/resolution and need for revision to consent form and/or other study documentation) will be completed.

All Serious Adverse Events, regardless of causal relationship to the investigational product, will be forwarded to **Merck Worldwide Product Safety** via fax (**[contact]**) within 2 working days of the investigator becoming aware of the event and no later than 3 calendar days.

The Principal Investigator is expected to provide as much of the following information:

- Protocol name and number
- Subject identifiers (no PHI will be shared with the IRB, unless requested)
- Demographic data
- Nature of the event
- Severity of the event
- Probable relationship (causality) of AE to study procedure
- Date and time of AE onset
- Date and time of AE resolution, if available
- Concomitant medications that the participant was taking for an underlying medical condition or disease and the therapeutic agents used for the treatment of the adverse event
 - Clinical assessment of participant conducted at time of SAE/AE
 - Results of any laboratory and/or diagnostic procedures, and treatment
 - Follow-up plan
 - Outcome
 - Autopsy findings (if appropriate)

The Principal Investigator will provide details about the AE/ADE as they become available. If additional information cannot be obtained for whatever reason, this will be documented. The Principal Investigator should inform the IRB when no other information is expected. The Principal Investigator should provide the IRB with a logical, complete, and accurate narrative description of the SAE based upon the above information.

The Principal Investigator should promptly determine an assessment of causality

The IRB determines if any corrective actions should be initiated as a result of any known specific or collective SAE/AE(s) and inform the principal investigator of the corrective action (e.g., revision of informed consent form, protocol, CRF).

The Principal Investigator/designee should keep originals or photocopies of all relevant documentation, including facsimile confirmations, and file them in the participant's file.

The Principal Investigator should ensure that all routine AE(s) are reported as part of the periodic or annual reporting requirements to the IRB of record.

The Principal Investigator should file copies of all correspondence with the IRB in the appropriate section of the Regulatory Master File or site study file.

Other Reportable Events:

The following events are also reportable to the IRB:

- Any adverse experience that, even without detailed analysis, represents an unexpected SAE that is rare in the absence of drug exposure (such as agranulocytosis, hepatic necrosis).
- Any AE that would cause a modification to the investigators brochure, protocol or ICF, or would prompt other action by the IRB to assure protection of human subjects.
- Information that indicates a change to the risks or potential benefits of the research, in terms of severity or frequency. For example:
 - An interim analysis indicates that participants have a lower rate of response to treatment than initially expected.
 - Safety monitoring indicates that a particular side effect is more severe, or more frequent than initially expected.
 - A paper is published from another study that shows that an arm of your research study is of no therapeutic value.
- Breach of confidentiality
- Change to the protocol taken without prior IRB review to eliminate apparent immediate hazard to a research participant.
- Incarceration of a participant when the research was not previously approved under Subpart C and the investigator believes it is in the best interest of the subject to remain on the study.
- Complaint of a participant when the complaint indicates unexpected risks or the complaint cannot be resolved by the research team.
- Protocol violation (meaning an accidental or unintentional deviation from the IRB approved protocol) that in the opinion of the investigator placed one or more participants at increased risk, or affects the rights or welfare of subjects.

Unanticipated Problem Involving Risks to Subjects or Others (UPRSO): Any incident, experience, or outcome that meets **all** of the following criteria:

- 1)Unexpected (in terms of nature, severity, or frequency) given a) the research procedures that are described in the protocol-related documents, such as the IRB-approved research protocol, informed consent document, or investigators brochure; and b) the characteristics of the subject population being studied;
- 2)Related or possibly related to participation in the research (possibly related to participation in the research means there is a reasonable possibility that the AE, experience, or outcome may have been caused by the procedures involved in the research.); and
- 3)Suggests that the research places subjects or others at a greater risk of harm (including physical, psychological, economic, or social harm) than was previously known or recognized.

12.8. Subject Withdrawal

A subject has the right to withdraw from the study entirely at any time for any reason without prejudice to future medical care by the investigator or other physician. The investigator also has the right to withdraw subjects from the study in the event of concurrent illness, AEs, or other reasons deemed to be in the subject's best interest.

Subjects **must be withdrawn** from the trial (treatment and procedures) for the following reasons:

- Subject withdraws consent for study treatment and study procedures. A subject must be removed from the trial at his/her own request or at the request of his/her legally acceptable representative. At any time during the trial and without giving reasons, a subject may decline to participate further. The subject will not suffer any disadvantage as a result.
- Subject becomes pregnant while undergoing treatment with Zepatier—therapy will be stopped as there are no human safety data of Zepatier during pregnancy. There are no adequate and well-controlled studies with Zepatier in pregnant women. No effects on embryo-fetal development were observed in rats or rabbits at grazoprevir or elbasvir exposures higher than exposures in humans at the recommended clinical dose. Because animal reproduction studies are not always predictive of human response, Zepatier should be used during pregnancy only if the potential benefit justifies the potential risk to the fetus. Because the transmission rates of HCV from mother to fetus are very small, and HCV can be treated after pregnancy and delivery, therapy will not be continued during pregnancy. Patients will continue with the regularly scheduled study visits, but will not be eligible to receive continued Zepatier therapy.
- Subject develops a condition that it is life threatening or any other significant risk as judged by the Investigators. Patients will not receive study drug, but will continue with study visits as scheduled.
- Zepatier is no longer produced by the company, or if a decision is made to stop the study patients will not receive study drug, but will continue with study visits as scheduled.

Any subject removed from the trial will remain under medical supervision until discharge or transfer is medically acceptable.

In all cases, the reason for withdrawal must be recorded in the CRF and in the subject's medical records.

In order to preserve the integrity of the intention-to-treat analysis, even if the subject is withdrawn from the treatment portion of the protocol (either due to subject, physician, or investigator decision), it is imperative to continue with the scheduled follow-up assessments both for the safety of the subject and for completeness of data collection. This will be explained to potential subjects at the time of informed consent. The importance of adherence with study visits will be reinforced throughout the trial. If the treatment is permanently withdrawn, the subject will return to the center for safety assessment (history, physical examination, and clinical laboratories, if necessary).

12.9. Confidentiality of Study Data

Information about study subjects will be kept confidential and managed according to the requirements of the Health Insurance Portability and Accountability Act of 1996 (HIPAA). Those regulations require a signed subject authorization informing the subject of the following:

- What protected health information (PHI) will be collected from subjects in this study
- Who will have access to that information and why
- Who will use or disclose that information
- The rights of a research subject to revoke their authorization for use of their PHI

In the event that a subject revokes authorization to collect or use PHI, the investigator, by regulation, retains the ability to use all information collected prior to the revocation of subject authorization. For subjects that have revoked authorization to collect or use PHI, attempts should be made to obtain permission to collect at least vital status (i.e., that the subject is alive) at the end of their scheduled study period.

Should direct access to medical records require a waiver or authorization separate from the subject's statement of informed consent, it is the responsibility of the Investigator to obtain such permission in writing from the appropriate individual.

12.10. Potential Risks

12.10.1. Risks of Study Procedures

There are several areas of potential risk in this study. We will obtain several blood samples from each subject. There is a risk of bruising, hematoma, and infection after phlebotomy, which are possible but not considered serious AEs. Fainting may occur, which is unlikely but considered a serious AE. The removal of <70 cc of blood every 1-4 weeks during the 40-week post-transplant period is a potential risk; however this amount is routinely taken from subjects for clinical indications without adverse effect. Study medications will be delayed until after phlebotomy on each study day.

Because we may store subjects' blood samples, there may be confidentiality risks associated with the storage and analysis of those samples or the information resulting from the analysis of those samples. Samples may be used for genetic testing. Under some circumstances, it can be a risk for genetic information to be known. To help ensure confidentiality, samples will be coded and stored in a secured facility. While situations cannot be foreseen where potentially sensitive genetic information is revealed or where people who should not have this information could obtain it (representing a loss of confidentiality), however, it is possible that presently unforeseen situations may arise where this could happen.

The risk of undergoing screening includes potential identification of new health problems that subjects were unaware of. If we discover new health problems, we will answer subjects' questions and try to arrange appropriate treatment if any is needed. If new health problems are discovered, it is possible that subjects would not be able to enter this study. It is also possible that subjects would no longer be eligible for heart transplantation based on the results.

The risks of heart transplant surgery include blood loss, infections, and deep vein thrombosis. There are also risks related to immunosuppression and standard anti-infective therapy.

The risks of any transplant include primary graft non-function, delayed graft function, acute rejection, and death. Re-admissions within 30 days after a heart transplant are expected in approximately 40% of patients.

There may also be a small risk of developing Focal and Segmental Glomerulosclerosis (FSGS) after receiving a heart from a HCV positive donor. However, this condition can also develop in patients who do not have HCV. After transplant, we will monitor all patients for FSGS and similar conditions.

12.10.2. Risk of Genotyping Failure

There is a risk of failure of the Genotyping LDT in that no result is obtained. However, the risk to the recipient participant, in this event, is that they would not receive the transplant. Hence, the related risk is losing the opportunity to use the organ. Failure of the LDT could be due to an instrument or cartridge failure or issues with the sample (e.g., the sample contains a very low level of virus). To minimize the study impact of a failed cartridge, the HUP Molecular Pathology Laboratory will run the study samples in duplicate due to there not being enough time to repeat the test (as would be done with a sample in clinical care). The duplicate sample

testing will serve to provide additional confirmation of the result because the RNA extraction will be performed twice. Thus, confirmation testing will be performed on every sample in the study with a single result generated.

There is also a risk of the Genotyping LDT giving an incorrect genotype. The risk to the recipient participant, in this event, is that they receive the transplant, but are possibly unable to be adequately treated for HCV positivity. Failure of the LDT to give an accurate genotype could be due to a mixed infection (e.g. genotype 1 and 2) or HCV genotype 4f infection in the donor sample.

12.10.3. Risk of NS5a Drug Resistance Test Failure

The potential risks of the NS5a resistance testing are false negative and false positive test results. The risk of a false negative test result would be if the test does not report any one of the four pertinent polymorphisms, even though they are present (the presence of which would be rare). In this case, the patient would receive only 12 weeks of Zepatier (rather than 16 weeks of Zepatier + renal-dosed Ribavirin), and potentially fail first-line therapy, requiring second-line therapy.

A false positive result is less likely to happen than a false negative result. The risk of a false positive test result would be if the test reports a polymorphism when the subject does not have one. Hence, the subject would be exposed to Zepatier for 4 weeks longer than needed as well as Ribavirin, and potentially experiencing the products' side effects.

12.10.4. Risk of Study Drugs

Zepatier

In subjects receiving Zepatier for 12 weeks, the most commonly reported adverse reactions of all intensity (greater than or equal to 5% in placebo-controlled trials) were fatigue, headache, and nausea. In subjects receiving Zepatier with ribavirin for 16 weeks, the most commonly reported adverse reactions of moderate or severe intensity (greater than or equal to 5%) were anemia and headache.¹⁵⁻¹⁷ The greatest risk is failure to achieve SVR12 after treatment with Zepatier, leading to chronic HCV.

There is a risk of fetal harm and birth defects should any woman taking Zepatier become pregnant while on the drug.¹⁵⁻¹⁷ Due to the age of the participants, this is a small risk, as all will be over 40 and unlikely to become pregnant. However, to mitigate this risk, all pre-menopausal women with a uterus will be screened for pregnancy before enrollment and instructed to use a highly effective form of birth control (e.g. abstinence, intrauterine device, etc.). Highly effective forms of birth control will be defined by the Mycophenolate Risk Evaluation and Mitigation Strategy (REMS), a standard protocol used for post-transplant patients at Penn being treated with Mycophenolate.

Sovaldi (Sofosbuvir)

The most common adverse events (incidence greater than or equal to 20%, all grades) observed with Sovaldi in combination with ribavirin were fatigue and headache. The most common adverse events observed with Sovaldi in combination with peginterferon alfa and ribavirin were fatigue, headache, nausea, insomnia and anemia.¹⁸

Ribavirin

The hemolytic anemia associated with ribavirin therapy may result in worsening of cardiac disease that has led to fatal and nonfatal myocardial infarctions. Significant teratogenic and embryocidal effects have been demonstrated in all animal species exposed to ribavirin. Therefore, ribavirin therapy is contraindicated in women who are pregnant and in the male partners of women who are pregnant.¹⁹

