7.1.4. Zepatier Initial Treatment Failures

Study subjects with treatment failure, defined as virologic breakthrough (when an undetectable viral load while on treatment becomes detectable) or virologic relapse (undetectable viral load after completion of treatment that during the 12-week post-treatment follow-up period becomes detectable) will be provided open-label Zepatier + Sofosbuvir (Sovaldi) 400 mg + Ribavirin (generic), renally dosed based on creatinine clearance per the manufacturer guidelines. Any subjects who experience treatment failure will repeat the original study lab visit and visit protocol once they begin their secondary treatment with Zepatier, sofosbuvir, and ribavirin, similar to

subjects initiating HCV treatment following heart transplantation. Prior to initiating treatment with this regimen, patients will have serum NS5A resistance (RAV) testing.

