8.1.2. Screening

The following procedures and activities will be performed during the screening process, after the informed consent is signed:

- Review medical history
- Vital signs
- Physical exam
- Review current medications
- Labs/phlebotomy: hepatic function panel, HCV RNA, HBV DNA, and HIV antibody
 - HBV Core Antibody will be checked in patients during screening, if not checked previously.
- Serum chg. pregnancy test (for women of childbearing potential)
- Completion of health status questionnaire (RAND-36)
- Provide instructions on recording of new medications and dose changes

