8.2. Study schedule of procedures

8.2.1. Visits, lab testing, and other clinical testing

See next page for table.

Transplanting HCV Hearts into HCV Negative Heart Recipients

Protocol V.2.0. 06/09/2017

		Visit Schedule			Research Visit Activities				Research Labs						Standard of Care						
Week(s) post-KT	Day(s) post-KT	Visit	Study Visits	Lab-Only	Informed Consent	Assess Adverse Events	Current Medications	RAND-36 Health Status Questionnaire	HBV DNA HIV AB & LFTs	HBV Core Antibody	Urine Preg Test	Urine Protein/Creatinine Ratio	HCV RNA	Viral Kinetics (optional)♦	NS5A Resistance	Genotyping	Vitals & Physical Exam	Surveillance biopsy	CMP*	CBC	Tacrolimus
Screening					✓	✓	✓		✓	✓	✓		✓			✓			✓		
1 (Begin treatment)	3 ± 1 day	V1	✓			✓	✓		✓	✓			✓	✓	✓	✓	✓	✓	✓	✓	✓
1	7 ± 1 day			✓			✓						✓	✓					✓	✓	✓
2	10 ± 1 day	V2	✓			✓	✓						✓	✓				✓	✓	✓	✓
2	14 ± 1 day			✓			✓						✓	✓				¥	✓	✓	✓
3	21 ± 3 day	V3	✓			✓	✓						✓	✓				✓	✓	✓	✓
4	28 ± 3 day	V4	✓			✓	✓	✓					✓	✓	✓			✓	✓	✓	✓
6	42 ± 7 day	V5	✓			✓	✓			✓			✓	✓				✓	✓	✓	✓
8	56 ± 7 day	V6	✓			✓	✓						✓	✓				✓	✓	✓	✓
10	70 ± 7 day	V7	✓			✓	✓							✓				✓	✓	✓	✓
12	84 ± 7 day	V8	✓			✓	✓			✓			✓	✓	✓			✓	✓	✓	✓
13 (End treatment)†	91 ± 7 day			✓			✓							✓							
16 (SVR 4)†	112 ± 14 day	V9	✓ †			✓	✓	✓					✓	✓			✓ †	✓	✓	✓	✓
20 (SVR 8)	140 ± 7 day			✓									✓	✓				✓	✓	✓	✓
24 (SVR 12)	168 ± 14 day	V10	✓			✓		✓					✓	✓	✓			✓	✓	✓	✓
28†	196 ± 7 day			✓										✓				✓	✓	✓	✓
32	224 ± 7 day			✓										✓				✓	✓	✓	✓
36 (SVR 24)	252 ± 7 day			✓									✓	✓	✓			✓	✓	✓	✓
40	280 ± 14 day			✓										✓				✓	✓	✓	✓
52	365 ± 14 day	V11	✓			✓							✓	✓	✓			✓	✓	✓	✓

* CMP=comprehensive metabolic panel which includes basic metabolic panel and liver function tests

Viral Kinetics testing can be done anytime there is a standard of care blood draw. Only if HRV Core Antibodies are positive.

If patients require the 16 weeks of therapy, the last 4 weeks would be the same as weeks 9-12 of

◆ Viral Kinetics testing can be done anytime there is a standard of care blood draw.

■ Only if HBV Core Antibodies are positive

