8.2.2. Blood sampling volumes

Maximum Post-Transplant Blood Draw Totals								
Week Post-KT	CBC	CMP	Tacrolimus	HBV Core Antibody	HCV RNA	Viral Kinetics (optional)♦	NS5A Resistance	Blood Draw Total
1	4	4.5	4	4	6	6	2	28.5
1	4	4.5	4	0	6	6	0	24.5
2	4	4.5	4	0	6	6	0	24.5
2	4	4.5	4	0	6	6	0	24.5
3	4	4.5	4	0	6	6	0	24.5
4	4	4.5	4	0	6	6	0	18.5
6	4	4.5	4	4	6	6	0	24.5
8	4	4.5	4	0	6	6	0	24.5
10	4	4.5	4	0	0	6	0	18.5
12	4	4.5	4	4	6	6	0	28.5
16	4	4.5	4	0	6	6	0	24.5
20	4	4.5	4	0	6	6	0	24.5
24	4	4.5	4	0	6	6	0	24.5
28	4	4.5	4	0	0	6	0	18.5
36	4	4.5	4	0	6	6	0	24.5
40	4	4.5	4	0	0	6	0	18.5
52	4	4.5	4	0	6	6	0	24.5
Total	68	76.5	68	0	84	102	2	400.5

♦ There may be additional blood draws due to optional Viral Kinetics lab testing increasing the total sample volume.

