12.4. Laboratory Values

The following clinical laboratory tests will be measured and repeated at time points specified in schedule of procedures (section 8.2.1) and as clinically indicated.

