12.4.3. Pregnancy Testing

Blood and urine pregnancy tests will be performed (as appropriate) per the schedule of procedures (section 5.2).

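### Section 12.10.4 calls ribavirin contraindicated in pregnant women and in men with a pregnant partner, but the visible protocol requires no pregnancy check when ribavirin is started

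*Combined protocol and SAP*

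**What the plan says.** **The contraindication.** Section 12.10.4 reports teratogenic and embryocidal effects of ribavirin in animals and concludes that "ribavirin therapy is contraindicated in women who are pregnant and in the male partners of women who are pregnant".

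**Where ribavirin is used.** Sections 7.1, 7.1.1 and 8.1.3.3.1 allow it first line, at the clinician's discretion, for subjects with the listed NS5A polymorphisms, up to week 16. Sections 7.1.1, 7.1.4 and 8.1.3.11 make it a fixed part of the 12-week second-line regimen after treatment failure.

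**Pregnancy testing.**
- Section 8.1.2 lists, among the screening procedures, a serum "pregnancy test (for women of childbearing potential".
- Section 12.10.4, under Zepatier, also places pregnancy screening before enrolment.
- The schedule in 8.2.1 has a column headed "Urine Preg Test". In the table as extracted, the only tick that falls under it is in the Screening row.
- Section 12.4.3 says "Blood and urine pregnancy tests will be performed (as appropriate) per the schedule of procedures (section 5.2".
- Section 12.4 has laboratory tests repeated at times "specified in schedule of procedures (section 8.2.1) and as clinically indicated".

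**Before second line.** Section 7.1.4 says that subjects who fail "will repeat the original study lab visit and visit protocol once they begin their secondary treatment". The one test it names as a precondition is NS5A resistance: "Prior to initiating treatment with this regimen, patients will have serum NS5A resistance (RAV) testing".

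**Contraception.** Section 6.2.1 requires a barrier method or abstinence after transplant for both sexes. Sections 7.1.1 and 8.1.3.3.1 require two methods for anyone on ribavirin, and for up to 6 months after the last dose.

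**The concern.** The protocol names a condition under which ribavirin must not be given, but attaches no required check for it to the decision to dispense. The one required test may be months old when ribavirin starts. For male subjects the contraindication concerns the partner, and no visible text asks about her at any time.

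What is at stake is fetal safety, not inference. A subject could be managed fully in line with the written plan and still begin ribavirin while pregnant or while his partner is pregnant. Section 12.10.4 reassures the reader that participants are over 40 and so unlikely to conceive, but that remark concerns women taking Zepatier. It does not cover the partners of male subjects, whose age the protocol does not limit.

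**Working it through.** The plan gives no figure to reproduce. The check sets the text on ribavirin beside the text on pregnancy, then dates the start of ribavirin relative to the only required test.

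**1. Is a check tied to starting ribavirin?**

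| Point in the plan | What the visible text requires |
|---|---|
| Screening (8.1.2, 12.10.4, Screening row of 8.2.1) | Pregnancy test in women of childbearing potential |
| Post-transplant visit lists (8.1.3.3 to 8.1.3.10) | No pregnancy test listed |
| First-line ribavirin (7.1, 7.1.1, 8.1.3.3.1) | NS5A result, clinician's decision, two contraceptive methods |
| Second-line ribavirin (7.1.4, 8.1.3.11) | NS5A retest, repeat of the study and laboratory visits, two contraceptive methods |
| Male subject's partner, any time | No question about an existing pregnancy |

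Repeating the visits for second line adds nothing here, because the visit lists being repeated contain no pregnancy test.

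**2. How much weight can the schedule table bear?** Limited weight. The table was read from PDF and conflicts with the text in places. Its Screening row shows no tick for RAND-36 or the physical exam, which 8.1.2 requires. RAND-36 is unticked at visits 8 and 11, where 8.1.3.8 and 8.1.3.10 list it. NS5A is ticked at several later weeks, whereas 8.2.2 gives it a volume only in week 1. The table in 8.2.2, "Maximum Post-Transplant Blood Draw Totals", covers blood only, so it cannot show that a urine test is absent. The point therefore rests on 8.1.2, 12.10.4 and the visit lists; the schedule is merely consistent with them.

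**3. How old could the screening test be at second line?** Inputs: treatment starts in weeks 1 to 4 after transplant (8.1.3.3); the course is 12 or 16 weeks (7.1); relapse is defined within 12 weeks after treatment (7.1.4), with draws at about 4 and 12 weeks (8.1.3.8).

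Week of detection = start week + course length + weeks after treatment.

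| Course | 4-week draw | 12-week draw |
|---|---|---|
| 12 weeks | 1+12+4 = 17 to 4+12+4 = 20 | 1+12+12 = 25 to 4+12+12 = 28 |
| 16 weeks | 1+16+4 = 21 to 4+16+4 = 24 | 1+16+12 = 29 to 4+16+12 = 32 |

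A relapse found at these draws thus falls 17 to 28 weeks after transplant, or 21 to 32 weeks with the longer course. The screening test is older still by the waitlist time, which is not given. Breakthrough on treatment and first-line ribavirin come sooner; the turnaround of the NS5A test is not given. These weeks describe the age of the test, not a probability of harm.

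**4. How many subjects could be affected?** About 10 are treated. Section 7.1 cites 94 to 100% SVR-12. If that held here, which is an assumption because those figures are not from this trial's population, the expected number without SVR-12 would be 10 × (1 − 1.00) = 0 to 10 × (1 − 0.94) = 0.6. The frequency of the polymorphisms that lead to first-line ribavirin is not stated; 12.10.3 appears to call them rare. The number who would receive ribavirin while pregnant, or with a pregnant partner, cannot be estimated from the documents.

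**The case against.** The best reply is that the plan is not silent. Pregnant women are excluded at entry (6.2.2). During the waitlist, records are reviewed monthly and subjects contacted every 6 to 8 weeks, and a newly arising exclusion is to be captured (12.7.3). Reactivated subjects have their eligibility reviewed again (6.1). The treating physician judges whether starting treatment is safe (8.1.3.3), and first-line ribavirin needs a further clinical decision by a prescriber who has the contraindication in the protocol. Investigators may order extra tests for safety (8.1.3.2), and 12.4.3 foresees both blood and urine tests. The qualifier there could mean women of childbearing potential rather than mere discretion. Pregnancy during treatment stops Zepatier (12.8).

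Much of this stands, and it is why the severity is low. It does not close the gap. Contraception prevents a new pregnancy but does not reveal an existing one. The physician's judgment and the extra-testing clause permit a check without requiring it. On either reading of its qualifier, 12.4.3 defers to a schedule in which no post-screening test can be identified. The stopping rule in 12.8 mentions neither ribavirin nor partners.

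A reader might be tempted to go further in three ways, none of which the documents support:
- **An exact count of empty cells in the urine pregnancy column.** The extracted table is too unreliable for that.
- **A required test when Zepatier is started.** The stated contraindication concerns ribavirin. Section 12.8 reports no embryo-fetal effects of Zepatier in animals and does not call it contraindicated, although 12.10.4 does mention a fetal risk.
- **Significance in the section number cited by 12.4.3**, which leads to the specific aims. That is clerical.

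**Conclusion.** The point holds, with low severity. The visible protocol declares a contraindication to ribavirin and requires a pregnancy test only at screening. It requires no pregnancy test and no partner question when ribavirin is started in either line. The partner part is the clearer of the two, since no check of any kind is visible for men.

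The size is small: about 10 treated subjects aged 40 to 65, with ribavirin confined to those with NS5A polymorphisms or treatment failure. The possible harm to a fetus is serious, but its expected frequency cannot be computed here.

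It would be wrong to infer that the plan intends or tolerates ribavirin in pregnancy, or that the primary result is compromised. The protocol states the contraindication and surrounds it with contraception rules, and neither the SVR-12 definition nor its analysis plan is touched.

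The conclusion rests on the visible text. The consent form, the mycophenolate REMS and the ribavirin label are not in the documents and could contain a check. The protocol itself invokes the REMS only for contraception.

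**What to change.** In 7.1.1, 7.1.4 and 8.1.3.3.1, add a condition that must be met immediately before ribavirin is first dispensed, in first or second line: a negative urine pregnancy test for women of childbearing potential and, for men, confirmation that the partner is not pregnant. Withhold ribavirin if the condition is not met.

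**Cost.** At most one check per line, so 1 + 1 = 2 per subject who receives ribavirin in both lines, and no more than 10 × 2 = 20 in the whole trial even if every treated subject did. These are urine tests or questions at existing dispensing contacts.

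**Optional extension.** Repeat the check at each 28-day ribavirin dispensing. That is at most 112/28 = 4 first line plus 84/28 = 3 second line, or 7 per subject.

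**Downside.** Rarely, a subject will be unable to receive ribavirin. In first line the plan already leaves ribavirin to the clinician. In second line, 7.1.4 names no other regimen, so the investigators should decide beforehand what such a subject would be offered.
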